3 STATISTICAL METHODOLOGY

3.1 General Considerations

3.1.1 *Study Day*

Study day will be calculated from the date of first dose of study drug, as actual visit date – first dose date + 1. The day of the first dose of study drug will be Day 1, and the day immediately before and after Day 1 will be Day -1 and Day 2.

3.1.2 *Analysis Visits*

Subject visits might not occur on protocol-specified days. Therefore, for the purpose of analysis, all scheduled, unscheduled, and early termination visits will be assigned to analysis visits according to the analysis windows ([Appendix 1](#)) based on study days. If there is more than 1 assessment in an analysis window, the assessment closest to the target day will be used in the analysis. If there are 2 assessments in a window equidistant from the target day, the later assessment will be used in the analysis.

3.1.3 *Definition of Baseline*

Baseline is defined as the last non-missing measurement prior to the first dose of study treatment. This can be on Day 1 as long as the measurement is taken prior to the first dose.

3.1.4 *Summary Statistics*

Summary statistics will be presented. Unless otherwise stated, continuous variables will be summarized using the number of non-missing observations, arithmetic mean, standard deviation, median, minimum, and maximum values as descriptive statistics. Categorical variables will be summarized using the frequency count and the percentage of patients in each category as descriptive statistics.

3.1.5 *Handling of Dropouts and Missing Data*

In general, data will be analyzed and presented as observed and will not be imputed for the analysis of efficacy and safety, unless otherwise specified.

In case the start and end dates for adverse events and concomitant medications/procedures are missing or incomplete, the missing component(s) will be assumed as the most conservative value possible. For example, AEs with missing start dates, but with stop dates either overlapping into the treatment period or missing, will be counted as treatment-emergent, taking the worst-case approach. When partial dates are present in the data, both a partial start date and/or a partial stop date will be evaluated to determine whether it can be conclusively established that the AE started prior to the start of study treatment or ended prior to the start of study treatment. If the above cannot be conclusively established based on the partial and/or present dates, then the AE will be considered as treatment-emergent. Actual data values as they appear in the original case report forms (CRFs) will be presented in the data listings.

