2.3.2 Secondary Efficacy Endpoints

The key secondary endpoint is the number of clinically significant infections or episodes of end-organ disease per patient due to AdV, BKV, CMV, EBV, HHV-6, or JCV through Week 26.

The other secondary endpoints include:

- Clinically significant infections or episodes of end-organ disease per patient due to AdV, BKV, CMV, EBV, HHV-6, or JCV from each individual virus through Week 14 and Week 26 (6 endpoints each at Week 14 and Week 26)
- Mean viral load for AdV, BKV, CMV, EBV, HHV-6, and JCV for each individual virus through Week 14 and Week 26, obtained as AUC/number of days (6 endpoints each at Week 14 and Week 26)

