3.4.2 Secondary Efficacy Endpoints

The key secondary endpoint is the number of clinically significant infections or episodes of end-organ disease per patient due to AdV, BKV, CMV, EBV, HHV-6, or JCV through Week 26. The definition of clinically significant infections or episodes is the same as for the primary endpoint. The summary statistics will be provided by each individual virus at Week 14 and 26, respectively.

Similar analysis will be performed for the clinically significant infections or episodes of end-organ disease per patient due to AdV, BKV, CMV, EBV, HHV-6 or JCV, from each individual virus through Week 14 and Week 26 (i.e., 6 endpoints each at Week 14 and Week 26).

The mean viral load for each AdV, BKV, CMV, EBV, HHV-6, and JCV virus, obtained as AUC/number of days at Week 14 and Week 26, will be summarized by descriptive statistics in the original and log10 scales. For each virus, the viral load and change from baseline over time will also be summarized in the original and log10 scales.

By-patient listings will be provided for the clinically significant infections or episodes of end-organ disease per patient due to AdV, BKV, CMV, EBV, HHV-6, or JCV.

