3.4.3 Exploratory Efficacy Endpoints

The exploratory efficacy endpoints are listed in Section 2.3.3.

The observed and change from baseline in QoL assessments will be summarized through Week 26. Listings will be provided for the QoL assessments.

Since most of the patients are undetectable, the number and percentage of patients with detectable viremia (i.e., \geq LLOQ) will be summarized at Week 14 as well as by visit and at any visit.

By-patient listing will be provided for AdV, BKV, CMV, EBV, HHV-6, and/or JCV viremia and QoL measures.

Subgroup analyses may be conducted for the efficacy endpoints by type (class I or II), the number of HLA matches, and letermovir treatment at Baseline.

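### Read literally, SAP 3.1.2 drops or swaps required viral-load samples in the AUC endpoint; separately, post-infusion Day 1 ECG and vital signs fall in the baseline row

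*SAP*

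**What the plan says.** **Windowing.** SAP 3.1.2 states that "all scheduled, unscheduled, and early termination visits will be assigned to analysis visits according to the analysis windows". It then keeps one value: "If there is more than 1 assessment in an analysis window, the assessment closest to the target day will be used in the analysis". For ties, "If there are 2 assessments in a window equidistant from the target day, the later assessment will be used in the analysis". Appendix 1 Table 2 gives windows specifically for viral load.

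**Endpoint.** SAP 2.3.2 and 3.4.2 define 12 secondary endpoints: mean viral load for six viruses at Weeks 14 and 26, "obtained as AUC/number of days at Week 14 and Week 26, will be summarized by descriptive statistics in the original and log10 scales". Neither section says which samples enter, how the area is integrated, how results below the LLOQ are valued, or what the number of days is. SAP 3.1.5 says "In general, data will be analyzed and presented as observed and will not be imputed for the analysis of efficacy and safety", and 3.4.3 remarks "Since most of the patients are undetectable".

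**Required extra samples.** Protocol 8.3.2 requires a central-laboratory sample on the day antiviral therapy starts. If a local result prompted the therapy, a second sample is required 48-72 hours later.

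**Day 1.** Protocol 8.4.3 places the ECG within one hour after infusion on dosing days. Protocol 6.1.2 repeats vital signs at the end of infusion and 15, 30, 45 and 60 minutes later. SAP 3.1.3 takes baseline as the last pre-dose value: "This can be on Day 1 as long as the measurement is taken prior to the first dose". SAP Appendix 1 Tables 3 and 4 give Study Day 1 a single row, Day 1/Baseline, and the next window opens on Day 2.

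**Related items.** SAP 3.5.5 summarises QTcB only, although Protocol 8.4.3 has the machine provide both corrections. In the follow-up schedule (Protocol Table 4, SAP Table 8) the EBV cell at Week 26/ET is blank. Footnote a of the same table asks for an EBV sample at early termination, and SAP 2.3.2 plans an EBV mean through Week 26.

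**The concern.** Samples taken when therapy starts are likely to carry the highest loads. If the by-visit rule also governs the AUC, whether such a sample counts, is ignored or replaces the visit sample depends on its distance from a target day. The resulting mean can be too low or too high. Two programmers following the same SAP could produce different values for 12 secondary endpoints.

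On the safety side, a row labelled as baseline would hold values taken after the first infusion. That infusion would then have no correctly labelled post-dose summary.

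**Working it through.** **1. Inputs.** From SAP Appendix 1 Table 2, target (window): Week 1, 8 (2-11); Weeks 2-13, targets 15, 22 ... 92 (target -3 to +3); Week 14, 99 (96-127); Week 22, 155 (128-169); Week 26, 183 (after 169). Each upper limit is the midpoint to the next target, rounded down: (8+15)/2 = 11.5 gives 11, (99+155)/2 = 127, (155+183)/2 = 169. Scheduled days from SAP Appendix 2 are 1, 8, 14, 21 ... 98, 154, 182. From Week 2 on, each target lies one day after the scheduled day.

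**2. Day counts, patients aged 12 or over, visits on schedule.** With a visit on day s and a target of s+1, an extra sample wins only on day s+1 (distance 0) or s+2 (tie, later wins).

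- Days 2-98: 97 days less 14 visit days = 83. Dropped: 9 (Week 1) + 12 x 4 (Weeks 2-13) + 2 (Days 96-97) = 59. Displacing: 12 x 2 = 24.
- Days 99-182: 84 days less 2 visit days = 82. Dropped: 27 (Days 101-127) + 39 (Week 22 window) + 12 (Days 170-181) = 78. Displacing: Days 99, 100, 155 and 156 = 4.

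Under 12 years, five viruses are sampled mostly every other week. In Days 2-98 that leaves 97 - 8 = 89 non-visit days: 30 dropped, 14 displacing, 45 filling an otherwise empty window.

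**3. Week 18.** Day 126 has an infection assessment but no scheduled viral load, and it lies inside the Week 14 window. If Week 14 was on Day 98, a Day 126 sample is dropped (distance 27 against 1). If Week 13 was on Day 91 and Week 14 on Day 95 (permitted, -3 days), Day 95 falls in the Week 13 window and loses to Day 91. The Day 126 sample then becomes the Week 14 value.

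**4. Direction, with assumed loads and linear trapezoids.** Loads 0; 500; 50,000; 20,000; 5,000; 500.

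- Example A, Days 15, 22, 25, 27, 29, 36. All samples: 1,750 + 75,750 + 70,000 + 25,000 + 19,250 = 191,750. Windowed (15, 22, 29, 36): 1,750 + 19,250 + 19,250 = 40,250, a ratio of 0.21.
- Example B, Days 14, 21, 22, 24, 28, 35. All samples: 1,750 + 25,250 + 70,000 + 50,000 + 19,250 = 166,250. Windowed (14, 22, 28, 35): 200,000 + 165,000 + 19,250 = 384,250, a ratio of 2.31.
- Follow-up, 50,000 and 20,000 on Days 115 and 117, zero at all scheduled visits. All samples: 425,000 + 70,000 + 370,000 = 865,000, or 865,000/181 = 4,779 per day from Day 1 to Day 182. Windowed: 0.

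These show direction only; the documents give no loads.

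**5. Unstated AUC rules.** If the last sample is on Day 49, dividing by 97 days (Day 1 to 98) rather than 48 (Day 1 to 49) gives 48/97 = 0.49 of the mean. For a patient with every sample below the LLOQ, a value of 0 makes log10 undefined. LLOQ/2 gives log10(25) = 1.40 to log10(250) = 2.40 for an assumed LLOQ of 50-500 copies/mL (not in the documents).

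**6. Day 1.** A post-infusion value on Study Day 1 meets only the 1-1 window. If a pre-dose vital sign was taken the same day, all values are at distance 0, and the later-wins rule selects a post-dose one. That rule mentions only two assessments; up to six sets may exist (one before, five after). The Day 1 ECG is post-dose, so the 3.1.3 baseline would normally be the screening ECG while the baseline row shows the Day 1 value.

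**7. QTc.** QTcB = QTcF/(60/HR)^(1/6). At an assumed constant QTcF of 400 ms, heart rate 80 to 100 moves QTcB from 400/0.75^(1/6) = 419.6 to 400/0.6^(1/6) = 435.5, or +15.9 ms.

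**The case against.** The strongest reply is that 3.1.2 exists because visits miss their planned days, so it is a rule for by-visit tables. SAP 3.4.2 treats the AUC mean separately from viral load over time. Elsewhere the SAP uses other selection rules: the last pre-dose value (3.1.3), the worst post-baseline value (3.5.3) and detection at any visit (3.4.3). A programmer could reasonably use every sample. This stands in part. A reader might infer that the AUC is built from windowed records; no sentence says so. What remains is that the literal text leads there and nothing excludes it.

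A reader might also turn 59 of 83 into a 71% loss of samples. The documents do not support that. Infection assessment is scheduled weekly during treatment, a sample on a visit day is not an extra one, real visits vary within their windows, and the number of off-schedule samples is not given.

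A third inference would be that the all-sample AUC is the correct one. It is not unbiased, because sampling is triggered by suspected infection. In the follow-up example, 425,000 + 370,000 = 795,000 of the 865,000 (92%) comes from straight lines drawn across long gaps. Scheduled-only sampling has the opposite weakness: there is no viral-load visit between Days 98 and 154.

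On Day 1, change from baseline is protected by 3.1.3 and the by-patient listings keep every value, so the fault lies in the summary rows and their labels.

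**Conclusion.** The point holds in this form. Followed literally, 3.1.2 with Table 2 lets the calendar decide whether a sample required by Protocol 8.3.2 is ignored or replaces a scheduled value, and the mean can move either way. The SAP is also open to a narrower reading, so it must say which applies. The missing integration, below-LLOQ and day-count rules need settling under either reading.

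The day counts rest on complete, on-time schedules. The loads, LLOQ, heart rates and QTcF are assumptions, so none of the examples measures the effect in this trial. The remark in 3.4.3 about undetectable patients introduces the detectability summary and gives no share of patients who were never positive.

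The reach is limited. The primary and key secondary endpoints are investigator-determined infections and are untouched. What is affected is the viral-load means and the ECG and vital-sign summaries in a single-arm descriptive cohort of 25 to 35 patients. It should be corrected, but it does not threaten the trial's main result.

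**What to change.** 1. State that 3.1.2 applies to by-visit tables only.
2. In 3.4.2, compute the AUC from central-laboratory samples at actual dates, by linear trapezoid from the 3.1.3 baseline. Name one below-LLOQ value (for example LLOQ/2, with 0 as an original-scale sensitivity). Define number of days as first to last sample used, ending at the Week 14 or Week 26 visit.
3. Report the all-sample and scheduled-samples-only AUC side by side. State that triggered sampling tends to overstate burden, that scheduled-only can miss follow-up episodes, and that neither is unbiased.
4. Restrict the baseline row to pre-dose values and add a Day 1 post-dose row for ECG and vital signs.
5. Report QTcF with QTcB. If QTcF was not captured, derive it as QTcB x (60/heart rate)^(1/6).
6. Reconcile the blank EBV cell at Week 26/ET with its footnote and the Week 26 EBV mean. If no sample was drawn, say that the EBV mean ends at the last sample.

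The cost is SAP wording and programming on existing data: one extra AUC table set, one extra row in the ECG and vital-sign tables, and one derived variable. No new collection is needed, but undrawn Week 26 EBV samples cannot be recovered. By-visit viral-load tables would still carry the one-day offset and the Day 126 case.

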3.2 Analysis Populations

3.2.1 *Enrolled Population*

The Enrolled Population will include all patients who signed the Informed Consent Form (ICF).

3.2.2 *Safety Population*

The Safety Population will include all patients who received ALVR105. All efficacy and safety analyses will be based on the Safety Population.

3.3 Patient Data and Study Conduct

3.3.1 *Patient Disposition*

Patient disposition information will be summarized using the Enrolled Population. The numbers and percentages of patients who were screened, screen failure along with the reasons of screen failure, not dosed, dosed, completed study drug, discontinued study drug early along with the reasons for early discontinuation of study drug, completed the study, and discontinued the study early along with the reasons for early discontinuation of study, received a Week 52 follow-up call will be summarized.

The numbers and percentages of patients in Safety Population with reason for exclusion will also be summarized.

By-patient listings will also be provided for patient disposition, screen failures, patients who were enrolled but not dosed, and reason for exclusion from analysis population.

3.3.2 *Protocol Deviations*

The numbers and percentages of patients with protocol deviations by deviation category will be summarized on Safety Population. All protocol deviations will be determined prior to database lock and listed by patient.

3.3.3 *Demographic and Baseline Characteristics*

Demographic (age, sex, race, and ethnicity) and baseline characteristics (height, weight, BMI, and childbearing potential at baseline) will be summarized with descriptive statistics or counts and percentages of patients as appropriate for safety population.

The following disease characteristics will also be summarized using frequencies and percentages: diagnosis, donor type, HLA alleles from the study patient, the allogeneic HCT donor(s), and the VST donor(s) as well as the number of shared alleles among these individuals, pre-conditioning therapy received, CMV serostatus at baseline of donor and recipient, letermovir use at Baseline, presence of Baseline viremia (based on central lab) and level of conditioning (myeloablative, reduced intensity, and non-myeloablative). A by-patient listing will be provided.

3.3.4 *Medical History*

Medical history will be coded to system organ class and preferred term using the Medical Dictionary for Regulatory Activities (MedDRA). The numbers and percentages of patients with

medical history by system organ class and preferred term will be summarized for safety population.

A by-patient listing of medical history will be provided.

3.3.5 Prior and Concomitant Medications

Concomitant medications will be coded to anatomical therapeutic chemical (ATC) class and preferred term using the WHO Drug Dictionary. All medications taken prior to the first dose of study treatment will be considered as prior medications. The medications taken prior to the first dose of study treatment and were ongoing or started on or after the first dose of study treatment will be considered as concomitant medications.

The numbers and percentages of patients taking prior and concomitant medications by ATC class and preferred term will be summarized based on the Safety Population.

A by-patient listing will be provided for prior and concomitant medications.

3.3.6 Study Drug Exposure and Compliance

Study drug duration, number of doses, and total dosing will be summarized based on Safety Population.

The length of exposure to study drug will be calculated as the number of days from the first dose of study drug to the last dose of study drug plus 14 days, regardless if the patient missed one or more doses of study drug. Length of exposure will be summarized using descriptive statistics for the safety population.

A by-patient listing will be provided for study drug exposure.

Overall compliance will be calculated as:

$$(Sum \ of \ total \ vials \ administrated) / (total \ vials \ planned) * 100$$

The number and percentage of patients will be summarized for the Safety Population for the following categories: 0- <70% and >= 70%.

3.4 Efficacy Analyses

This section describes the analysis to be conducted on the primary, secondary and exploratory efficacy endpoints. The efficacy analyses for the Phase 2 OL cohort will be performed using the Safety Population.

3.4.1 Primary Efficacy Endpoint

The primary endpoint is the number of clinically significant infections or episodes of end-organ disease per patient due to AdV, BKV, CMV, EBV, HHV-6, or JCV through Week 14.

Clinically significant infections/episodes will be considered as a failure of prevention, thus, in calculating the value of this endpoint for a patient, each virus will be counted at most once, even if there are multiple infections/episodes for a given virus. Therefore, each patient could experience as many as 6 infections, one for each of the targeted viruses. In addition, a new onset is defined as a new clinically significant infection/episode that is not present at Baseline. Patients will be excluded from a particular virus of interest endpoint if they demonstrated clinically

significant infection with that virus at Baseline. Clinically significant infections include viremia requiring treatment and/or episodes of end-organ disease.

The number of clinically significant infections or episodes will be summarized using descriptive statistics.

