For the open-label portion of the study, similar endpoints will be analyzed. Additional details can be found in the Statistical Analysis Plan (SAP).

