9.4.2. Primary Efficacy Endpoint

The primary efficacy endpoint is:

- The primary efficacy endpoint is the proportion of patients with clinically significant AdV, BKV, CMV, EBV, HHV-6 and/or JCV infection (defined as clinically significant infection and/or end-organ disease as determined by an independent, blinded CAC through Week 14).

This endpoint will be summarized by cohort and treatment group using frequency counts and percentages.

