Time to onset of AdV, BKV, CMV, EBV, HHV-6, and/or JCV viremia will be calculated from the time of randomization until the first date of appearance of any observed viremia. Patients not observed with the onset of AdV, BKV, CMV, EBV, HHV-6, and/or JCV viremia will be censored. Patients who discontinued from the study early before the onset of AdV, BKV, CMV, EBV, HHV-6, and/or JCV viremia will be censored at the last assessment date for this endpoint. Patients who deceased prior to the onset of AdV, BKV, CMV, EBV, HHV-6, and/or JCV viremia will be censored at the last assessment date for this endpoint.

Kaplan-Meier plot for time to onset of AdV, BKV, CMV, EBV, HHV-6, and/or JCV viremia at Week 14 will also be provided for each treatment.

Categorical variables will be summarized using frequency counts and percentages. Continuous variables will be summarized by visit using descriptive statistics.

No adjustment for the multiplicity of secondary and exploratory endpoints will be made for this Phase 2 trial.

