2 STUDY OVERVIEW

2.1 Study Objectives

2.1.1 Primary Objective

The primary objective is to assess the efficacy of ALVR105 by the number of clinically significant infections or episodes of end-organ disease per patient due to AdV, BKV, CMV, EBV, HHV-6, or JCV through Week 14 as determined by the clinical investigators.

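### SAP 3.4.1-3.4.2: reported as observed, the single-arm infection count runs modestly low when patients withdraw, and it has no any-virus proportion or confidence interval

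*SAP*

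**What the plan says.** The SAP covers only the open-label cohort of 25 to 35 patients, all on ALVR105. Section 2.1.1 makes efficacy the aim: "The primary objective is to assess the efficacy of ALVR105 by the number of clinically significant infections or episodes of end-organ disease per patient".

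The endpoint in 3.4.1 is a count through Week 14. Each of the six viruses scores at most once, so a patient can score 0 to 6. A patient already infected with a virus at Baseline is not assessed on that virus. The analysis is then stated in full: "The number of clinically significant infections or episodes will be summarized using descriptive statistics". Section 3.1.4 limits this to n, mean, SD, median, minimum and maximum, or to counts and percentages for categorical variables. Section 3.4.2 carries the count to Week 26: "The definition of clinically significant infections or episodes is the same as for the primary endpoint".

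Two general rules apply. Section 3.2.2 says "All efficacy and safety analyses will be based on the Safety Population", meaning everyone dosed. Section 3.1.5, on dropouts and missing data, says "In general, data will be analyzed and presented as observed and will not be imputed for the analysis of efficacy and safety". Neither 3.4.1 nor 3.4.2 mentions death, withdrawal or time at risk. No any-virus proportion and no confidence interval is planned.

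In the protocol, the primary endpoint (9.4.2) is the proportion with any clinically significant infection: "This endpoint will be summarized by cohort and treatment group using frequency counts and percentages". Section 3 adds "For the open-label portion of the study, similar endpoints will be analyzed" and leaves the detail to the SAP. The only explicit rule for deaths is in 9.4.3, for time to onset of viremia: "Patients who deceased prior to the onset of AdV, BKV, CMV, EBV, HHV-6, and/or JCV viremia will be censored". The SAP has no such endpoint.

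**The concern.** With no control arm, the result will be read as an absolute level of infection under treatment. A patient who leaves at Week 5 without infection has been observed for only part of the 14 weeks, yet enters the mean as a full 0, so withdrawals pull the figure in the favourable direction.

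A mean count also mixes two things: how many patients were infected, and how many viruses each of them had. And a point estimate from 25 to 35 patients, printed without an interval, looks firmer than it is.

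**Working it through.** There is no plan figure to reproduce. The cohort size has no formula behind it, and the documents give no infection, withdrawal or death rate. The rates below are assumptions, shown over a range.

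**1. Early withdrawals scored as observed.** Let p be the 14-week risk at constant hazard, λ = −ln(1−p), and d the fraction withdrawing, at times uniform over 14 weeks and unrelated to infection. The average chance of being infection-free at exit is s = (1−e^(−λ))/λ = p/λ. The expected as-observed proportion is

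E = (1−d)p + d(1−s).

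For p = 0.30: λ = 0.3567, s = 0.30/0.3567 = 0.8411, 1−s = 0.1589.

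- d = 0.10: 0.9×0.30 + 0.1×0.1589 = 0.286, or 1.4 points low (−4.7%).
- d = 0.20: 0.8×0.30 + 0.2×0.1589 = 0.272, or 2.8 points low (−9.4%).

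At d = 0.20, a true risk of 20% reads as 18.1%, and 40% as 36.3%.

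The mean count is a sum of per-virus risks, so the same formula applies virus by virus. For per-virus risks of 2% to 40%, the relative shortfall is 5.0% to 4.6% at d = 0.10 and 10.0% to 9.2% at d = 0.20.

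**2. Deaths.** Put 20% dying and none withdrawing into the same formula. The as-observed figure is again 27.2%. Here that is also the true probability of infection before death, because follow-up is complete to death. A simulation (n = 30, 20,000 runs, p = 0.30, exits uniform) gave:

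| Withdraw / die | Competing-event target | As observed | Cumulative incidence, death competing | Deaths censored |
|---|---|---|---|---|
| 20% / 0 | 29.9% | 27.1% | 29.9% | 29.9% |
| 0 / 20% | 27.2% | 27.2% | 27.2% | 30.1% |
| 20% / 10% | 28.5% | 25.9% | 28.5% | 29.9% |

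Only withdrawal creates the shortfall, and the competing-event estimator removes it.

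**3. Mean against proportion.** A mean of 0.40 in 30 patients is 12 infections. That fits 12 patients with one virus each (40.0%), 6 with two (20.0%), 4 with three (13.3%) or 2 with six (6.7%).

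**4. Precision.** Exact (Clopper-Pearson) 95% intervals:

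- 0/25: 0 to 13.7%; 0/30: 0 to 11.6%; 0/35: 0 to 10.0%
- 5/25: 6.8% to 40.7%; 7/35: 8.4% to 36.9%
- 9/30: 14.7% to 49.4%, a width of 34.7 points

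A mean count of 0.50 (15 infections in 30 patients) has an exact Poisson interval of 8.40/30 to 24.74/30, or 0.28 to 0.82. This is illustrative, since infections within a patient may be correlated.

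**The case against.** The best defence is that the plan is less open than it looks. SAP 3.1.5 rules out imputation, 3.2.2 keeps all dosed patients in, and the only exclusion in 3.4.1 is infection with a given virus at Baseline. So the observed count is what will be reported, and its bias of 1.4 to 2.8 points at a 30% risk is small beside an interval about 35 points wide. This largely stands, and it is why the point is framed as a modest downward bias.

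A reader might infer something larger: that with no explicit rule the figure could move to 37% or 44%, the values at 10% and 20% withdrawing if infection-free leavers count as failures. The texts do not support that. Counting them as failures would be imputation, and 3.4.1 treats only infections or episodes as failures of prevention. Dropping leavers fits poorly with an all-dosed analysis set.

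The defence can also say that the any-virus figure is recoverable. The per-virus means are already proportions, a table of the 0-to-6 count would give it, and by-patient listings are planned. That is true, but per-virus figures do not determine the any-virus figure, and no such table is stated.

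Finally, no hypothesis or threshold is set for this cohort, and Protocol 4.2 describes the open-label period as a means to optimize procedures. The prespecification argument is limited too: SAP 1 describes these patients as already enrolled, treated and followed, and 3.4.3 already notes that most are undetectable. These points limit the weight of the concern. They do not remove it while SAP 2.1.1 states efficacy as the primary objective.

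**Conclusion.** The point holds as a recommended improvement to a single-arm estimate; it is not an error that undermines the analysis. Read naturally, SAP 3.4.1-3.4.2 understates the infection level by about 5% relative at 10% withdrawing and 9-10% at 20%. This assumes constant hazard, uniform exit times and withdrawal unrelated to infection. Imprecision is the larger matter, and the plan shows none of it. The mean count alone does not say how many patients were infected.

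Two further inferences are not supported. One is that scoring deaths as event-free hides failures: that scoring is consistent with a competing-event estimand and adds no bias. The other is that the protocol requires the any-virus proportion for this cohort. Protocol 3 promises only similar endpoints and defers to the SAP, Protocol 9.2 keeps the open-label cohort out of the primary statistical analysis, and SAP 1 bases the analysis on Amendment 4, so the change of endpoint may be deliberate. The case for the proportion is that it is informative.

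**What to change.** Keep the count and add to SAP 3.4.1-3.4.2:

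- **(a)** The observed n (%) of patients with at least one new-onset clinically significant infection from any virus through Weeks 14 and 26, with an exact 95% CI. Protocol 9.4.5 already uses this kind of interval for adverse events of special interest. The denominator is all dosed patients. A patient infected with one virus at Baseline stays in and is assessed on the other viruses. Label the table as counting early withdrawals as observed.
- **(b)** Any-virus cumulative incidence at Weeks 14 and 26 with 95% CI, with study withdrawals censored at last assessment and death as a competing event. Per-virus versions are optional. Note that this differs from the death censoring in Protocol 9.4.3, and why. It is feasible: under Protocol 7.3, patients who only stop therapy stay in follow-up, and those leaving the study have an early termination visit.
- **(c)** A 95% CI for the mean count (for example a patient-level bootstrap, or exact Poisson if there are no infections), and one sentence stating that withdrawals and deaths enter it with their observed count.

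No separate table of incomplete follow-up is needed, because SAP 3.3.1 already summarizes early discontinuation with reasons. The cost is SAP wording and a few extra tables from data already collected. The intervals will be wide, and the infection figure may be slightly less favourable. Censoring does not correct for withdrawal that is itself related to infection risk.
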